### 2.3.1. Risk Assessment

The safety profile of mavacamten treatment for participants with HCM is acceptable in the context of the observed clinical efficacy. Cumulatively (as of 30 October 2020), 97 total SAEs have been reported in 61 participants in the mavacamten clinical development program. Of these, 69 SAEs occurred in 45 participants treated with mavacamten and 28 SAEs occurred in 17 participants treated with placebo. Most serious and nonserious events reported for mavacamten-treated participants across the program were outcomes or symptoms of the underlying disease. No clinically significant off-target treatment effects were identified for mavacamten. In the pivotal Phase 3 study (MYK-461-005), dizziness was the most frequently reported AE and was more frequent in mavacamten-treated participants than placebo-treated participants. In the integrated safety summary, dizziness occurred in 15.5% of mavacamten treated participants and 12.2% of placebo treated participants. Given the absence of clear alternative etiology in a high proportion of participants, dizziness is proposed as an adverse drug reaction for mavacamten. Other proposed adverse drug reactions for mavacamten include heart failure and systolic dysfunction, which occurred in <5% of participants administered mavacamten. Systolic dysfunction with mavacamten has been reversible and has not resulted in a picture of progressive cardiac failure (recurrent hospitalizations and progressive LVEF reduction) as described in the literature associated with progression of underlying HCM.

Based on nonclinical data and the available clinical data, the most likely risks are those associated with higher exposures resulting in excessive decrease in cardiac contractility (decline in LVEF). Reduced tolerance might be reflected in nonspecific AEs such as fatigue or in reflex changes in resting heart rate (HR) or systolic blood pressure (BP). Higher exposures could result in the development of signs or symptoms of systolic heart failure, especially in the setting of simultaneous tachyarrhythmias or ischemia.

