### **8.2.5. Clinical Safety Laboratory Assessments**

Safety laboratory results will be assessed in an ongoing manner. See [Section 10.3](#) for the list of clinical laboratory tests to be performed and to the Schedule of Study Procedures ([Table 1](#)) for the timing and frequency.

- The investigator must review the laboratory report, document this review, and record any clinically significant changes occurring during the study as an AE. The laboratory reports must be filed with the source documents.

CONFIDENTIAL

Approved v2.0

- Abnormal laboratory findings associated with the underlying disease are not considered clinically significant unless judged by the investigator to be more severe than expected for the participant's condition.
- All laboratory tests considered clinically significant abnormal values during participation in the study should be repeated until the values return to normal or baseline or are no longer considered clinically significant by the investigator or study medical monitor.
  - If clinically significant values do not return to normal/baseline within a period of time judged reasonable by the investigator, the etiology should be identified, and MyoKardia or their designee notified.
  - All protocol-required laboratory tests, as defined in [Section 10.3](#), must be conducted in accordance with the laboratory manual and the Schedule of Study Procedures ([Table 1](#)).
  - If laboratory values from non-protocol specified laboratory tests performed at the institution's local laboratory require a change in participant management or are considered clinically significant by the investigator (eg, SAE or AE or dose modification), then the results must be recorded.

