#### **10.4.1.2. Adverse Events**

- According to the ICH guideline for GCP, an AE is defined as any untoward medical occurrence in a clinical investigation participant administered a pharmaceutical product; it does not necessarily have to have a causal relationship with this treatment.
- An AE can therefore be any unfavorable and unintended sign (eg, tachycardia, enlarged liver, clinically important or abnormal laboratory finding), symptom (eg, nausea, chest pain), or evidence of disease activity temporally associated with the use of a study medication, whether or not related to the study medication.
- Each AE should be recorded as a single diagnosis. Accompanying signs (including abnormal laboratory values or ECG findings) or symptoms should not be recorded as additional AEs. If a diagnosis is unknown, signs or symptoms should be recorded appropriately as a PTAE or AE.
- Any new disease or exacerbation of an existing disease (eg, a worsening in the character, frequency, or severity of a known condition) is an AE, except as described below:
  - Preexisting medical conditions (present at the time of signing of informed consent) are considered concurrent medical conditions and should not be recorded as PTAEs or AEs. However, if the participant experiences a worsening or complication of such a concurrent condition, the worsening or complication should be recorded appropriately as a PTAE (worsening or complication occurs before the first dose of study drug) or an AE (worsening or complication occurs after the first dose of study drug). Investigators should ensure that the event term recorded captures the change in the condition (eg, “worsening of ....”).
- Recurrence of an intermittent medical condition (eg, headache) not present prior to the first dose of study drug is an AE.

- Any deterioration in a laboratory value or other clinical test (eg, ECG, X-ray) that is associated with symptoms or leads to a change in study treatment or concomitant treatment or discontinuation from study drug is an AE.

The following additional points should be considered for PTAEs and AEs:

- Preplanned medical or surgeries or procedures
  - Preplanned surgeries or procedures that were scheduled prior to signing of informed consent are not considered PTAEs or AEs. However, if a planned procedure is performed early (eg, as an emergency) due to worsening of a preexisting condition, the worsening of the condition should be captured appropriately as a PTAE or AE.

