- Hospitalization for elective surgeries or procedures
  - Elective procedures performed for which there is no change in the participant's medical condition should not be recorded as PTAEs or AEs.
  - A hospitalization that was planned prior to the study or was scheduled during the study when the elective surgery or procedure became necessary because of the expected normal progression of the disease should not be recorded as PTAEs and AEs.
- Insufficient clinical response (lack of efficacy)
  - Insufficient clinical response, efficacy, or pharmacologic action should not be recorded as an AE. The investigator must make the distinction between exacerbation of preexisting medical condition and lack of therapeutic efficacy.
- Overdose
  - Cases of overdose with any medication without manifested side effects are not considered PTAEs or AEs.

The following should not be recorded as PTAEs or AEs:

- Any clinically significant abnormal laboratory findings or other abnormal safety assessments that are associated with the disease/disorder being studied, unless judged by the investigator to be more severe than expected for the participant's condition
- The disease/disorder being studied or expected progression, signs, or symptoms of the disease/disorder being studied, unless more severe than expected for the participant's condition
- Situations in which an untoward medical occurrence did not occur (social and/or convenience admission to a hospital)
- Anticipated day-to-day fluctuations of a preexisting disease or condition present or detected at the start of the study that do not worsen

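### The disease-progression exclusion in section 10.4.1.2 lets mild or moderate heart-failure worsening, a named risk of the drug, go unrecorded as an adverse event on undefined judgment

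*Combined protocol and SAP*

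**What the plan says.** Section 10.4.1.2 ends with a list of items that sites should not enter as pretreatment or on-treatment adverse events. One item is the studied disease itself and its "expected progression, signs, or symptoms of the disease/disorder being studied, unless more severe than expected" for that participant. Another covers clinically significant laboratory findings and other "abnormal safety assessments that are associated with the disease/disorder being studied, unless judged by the investigator to be more severe than expected". Section 8.2.5 repeats the laboratory part: "Abnormal laboratory findings associated with the underlying disease are not considered clinically significant unless judged by the investigator to be more severe than expected".

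Earlier in section 10.4.1.2 the direction is the opposite. "Any new disease or exacerbation of an existing disease" counts as an adverse event, subject to exceptions described beneath it. A sub-item requires worsening of a condition present at consent to be recorded under a term that shows the change. A further item makes a deteriorating laboratory value or clinical test an adverse event when it is symptomatic or alters treatment.

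On the drug's risks, section 2.3.1 states: "Other proposed adverse drug reactions for mavacamten include heart failure and systolic dysfunction, which occurred in <5% of participants administered mavacamten". It also warns: "Higher exposures could result in the development of signs or symptoms of systolic heart failure".

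Section 3 makes the frequency and severity of treatment-emergent adverse events part of the primary safety endpoint, with adverse events of special interest, serious adverse events, and laboratory, vital-sign and rhythm abnormalities. The synopsis describes a single open-label arm, and section 9.2 plans about 35 participants.

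**The concern.** A harm that the drug is suspected of causing can look the same as the disease being treated. A participant with more breathlessness or oedema may have drug-induced loss of contractility or progressing HFpEF. The list in section 10.4.1.2 lets the site leave the event out if it is thought to be expected progression. The investigator making that call knows that the participant is on mavacamten, has no written criterion, and has no control arm showing the usual course over 26 weeks.

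At stake is the count of non-serious heart-failure events in the primary safety endpoint. A worsening that was never entered is hard to recover at analysis. The study is meant to inform later HFpEF trials, so too low a count would carry forward into their risk assessment.

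**Working it through.** The plan gives no figure to reproduce: section 9.1 has no hypothesis test and section 9.2 no sample-size calculation. The main check is a comparison of the rules. The arithmetic only illustrates scale.

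**1. Which rule governs worsening heart failure?** Progression is a form of worsening, so the exacerbation rule and the progression exclusion both reach the same event. The exacerbation rule points to exceptions beneath it. What stands directly beneath it is the sub-item on pre-existing conditions, and that again requires worsening to be recorded. The not-to-record list comes later, and the section does not say whether the exceptions extend to it. The last item of that list separately excludes day-to-day fluctuation that does not worsen. Stable disease is therefore already covered, and what the disputed item adds is expected progression. The section also keeps insufficient clinical response out of the adverse events and asks the investigator to tell it apart from exacerbation, again without a criterion.

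**2. What is captured by another route?**
- Worsening judged more severe than expected: adverse event, through the exception in the exclusion itself.
- Test deterioration that is symptomatic or changes treatment: adverse event under section 10.4.1.2, although the item on disease-associated safety assessments competes with it.
- LVEF of 30% or less: adverse event of special interest (section 8.3.6).
- Death, life-threatening event or hospitalisation: serious adverse event (section 10.4.1.3), with no disease exemption in the definition. Section 10.4.2.2.5, however, starts from an event already recorded as a pretreatment or treatment-emergent adverse event, so an omission at the first step may carry over.
- Death: also summarised separately (section 9.4.4.1.1).
- NT-proBNP and hs-cTnT: primary pharmacodynamic endpoints, summarised by visit (sections 9.4.1 and 9.4.2). Laboratory values are summarised and out-of-range values listed whatever is entered as an adverse event (section 9.4.4.3).

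**3. What is left exposed?** Two groups remain: non-serious heart-failure worsening judged expected, and LVEF falls that are asymptomatic, change no treatment and stay above 30%. Entry requires LVEF of at least 60%, so a fall from 60% to 31% (60 − 31 = 29 points) does not meet the special-interest threshold. It would still be an adverse event if it led to a change in study drug. The thresholds for that are redacted.

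**4. Illustration of under-recording.** Inputs: n = 35 (section 9.2). The true event rate p is 5%, taken from the upper bound in section 2.3.1, with 2% and 10% added as assumptions. The share of events recorded by any route, s, is also an assumption. With participants independent,

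P(at least one recorded event) = 1 − (1 − p·s)^35.

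At p = 5%:
- s = 1: 1 − 0.95^35 = 83%; expected count 35 × 0.05 = 1.75
- s = 0.5: 1 − 0.975^35 = 59%; expected count 0.88
- s = 0.25: 1 − 0.9875^35 = 36%; expected count 0.44

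| True rate | All recorded | 75% | 50% | 25% |
|---|---|---|---|---|
| 2% | 51% | 41% | 30% | 16% |
| 5% | 83% | 74% | 59% | 36% |
| 10% | 97.5% | 93.5% | 83% | 59% |

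**The case against.** The strongest reply is that the rules can be read together: stable or expected disease is not recorded, worsening is. The exclusion carries its own exception, the exacerbation rule allows for exceptions, and the fluctuation item is limited to conditions that do not worsen. That reading is possible, but the text does not impose it. It leaves open what a site should do with mild or moderate worsening seen as ordinary progression.

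A reader might infer that the exclusion takes the drug's named risk out of the primary safety endpoint. The documents do not support that, because the routes in step 2 keep severe events in and systolic dysfunction has some capture of its own. A reader might also infer that a drug-related biomarker rise could be hidden. It could not: the exclusion affects adverse-event entry, not the measured values.

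A third tempting step is to say that losing one or two cases turns 1/35 or 2/35 into 0/35, lowering the exact 95% upper limit from 14.9% or 19.2% to 10.0%. That is a worst case. It needs every event to be missed, and nothing in the documents suggests so.

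Other points stand in part. The study is exploratory, an independent data monitoring committee reviews interim safety data (section 10.1.5.1), and section 6.8.2 requires medication changes to be entered with their reason, which leaves a trace. None of these puts an unrecorded event into the adverse-event tables.

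**Conclusion.** The point holds as a risk of under-counting. Section 10.4.1.2 gives two instructions for worsening heart failure, states no precedence, and leaves the choice to unblinded judgment without a criterion. This should be fixed, but it does not undermine the safety endpoint as a whole.

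The size is uncertain. With fewer than two events expected at a 5% rate, recording half of them would lower the chance of seeing any from 83% to 59%. This rests on an assumed recorded share and on a rate that is only an upper bound from the earlier programme, whose studies in section 2.2.1 enrolled HCM and healthy participants. The HFpEF rate may differ. The bound is also quoted for heart failure and systolic dysfunction in one sentence, although the latter has partly separate capture.

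Text around sections 7.1 and 8.3.6 is redacted and no separate SAP is in the file, so further capture of heart-failure events cannot be ruled out.

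**What to change.** Reconcile the two parts of section 10.4.1.2, and section 8.2.5 with them:

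- State that the disease-progression exclusion, including its part on safety assessments, does not apply to new or worsening heart failure or systolic dysfunction. These are recorded as adverse events whether or not they were expected.
- Keep the exclusion only for stable day-to-day fluctuation that does not worsen.
- Tabulate heart-failure and systolic-dysfunction events as a prespecified category in the safety analysis.
- Carry the same wording into the CRF completion guidelines.

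This changes what is recorded, not how participants are managed. The cost is about one paragraph in Appendix 4, a matching sentence in section 8.2.5, some extra adverse-event entries and a slightly higher reported rate. If the redacted text or the SAP already provides this capture, a cross-reference from section 10.4.1.2 would be enough.

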#### **10.4.1.3. Serious Adverse Event**

An SAE is defined as any untoward medical occurrence at any dose that:

CONFIDENTIAL

Approved v2.0

- Results in death
- Is immediately life-threatening (places the participant at immediate risk of death from the event as it occurred)
- Requires inpatient hospitalization or prolongation of existing hospitalization
- Results in persistent or significant disability or incapacity or substantial disruption of the ability to conduct normal life functions
- Results in a congenital abnormality or birth defect
- Is an important medical event that may not result in death, be life-threatening, or require hospitalization, but may be considered an SAE when, based upon appropriate medical judgment, it may require medical or surgical intervention to prevent any of the outcomes listed above

PTAEs that fulfill any of the criteria above are also to be considered SAEs and should be reported and followed up in the same manner.

- The terms “severe” and “serious” are not synonymous. Severity refers to the intensity of an AE (eg, rated as mild, moderate, or severe); the event itself may be of relatively minor medical significance (such as severe headache without any further findings).
- An AE of severe intensity need not necessarily be considered serious. For example, nausea that persists for several hours may be considered severe nausea but not an SAE. On the other hand, a stroke that results in only a limited degree of disability may be considered a mild stroke but would be an SAE.
- Severity and seriousness need to be independently assessed for each AE recorded on the eCRF.

SAEs are required to be reported by the investigator to MyoKardia or their designee within 24 hours after learning of the event.

#### **10.4.1.4. Adverse Events of Special Interest**

Symptomatic overdose, pregnancy, and LVEF  $\leq$  30% as determined by local site read echocardiogram are considered AESIs.

AESIs are required to be reported by the investigator to MyoKardia or their designee within 24 hours, irrespective of regulatory seriousness criteria.

#### **10.4.2. Collection and Reporting of Adverse Events**

##### **10.4.2.1. Pretreatment Adverse Events and Adverse Events Collection Periods**

Collection of PTAEs will commence from the time the participant signs the informed consent to participate in the study and continue until the participant receives the first dose of study drug. For participants who discontinue prior to study drug administration, PTAEs are collected until the participant discontinues study participation.

Collection of TEAEs will commence at the time the participant receives the first dose of study drug. Routine collection of TEAEs will continue until the end of the study. Assessments of the relationship of AEs to study drug will be captured for TEAEs and not PTAEs.

#### **10.4.2.2. Pretreatment Adverse Events and Adverse Events Reporting Periods**

At each study visit, the investigator will assess whether any subjective AEs have occurred. A neutral question, such as “How have you been feeling since your last visit?” may be asked. Participants may report AEs occurring at any other time during the study.

All participant experiencing PTAEs or TEAEs, whether considered associated with the use of the study drug or not, must be monitored until the symptoms subside and any clinically relevant changes in laboratory values have returned to screening levels or until there is a satisfactory explanation for the changes observed. All PTAEs and TEAEs will be documented in the PTAE/AE page of the eCRF, whether or not the investigator concluded that the event is related to the study drug. The information to be documented for each event is described in the following sections.

##### **10.4.2.2.1. Event Description**

When collecting PTAEs and TEAEs, the recording of diagnoses is preferred (when possible) to recording a list of signs and symptoms (eg, anemia, not low hemoglobin). However, if a diagnosis is known and there are other signs or symptoms that are not generally part of the diagnosis, the diagnosis and each sign or symptom will be recorded separately.

Death is an outcome and not the name of the event. In this situation, the event that led to the death is the name of the event.

##### **10.4.2.2.2. Start Date/Time and Stop Date/Time**

The date (and time during the period of residency) that the PTAE or TEAE started and the date (and time during the period of residency) that the event ended will be recorded. For events that continue for long periods of time, recording the end date as the day the event stabilized will be acceptable.

##### **10.4.2.2.3. Relationship to Study Drug (Suspected Adverse Reactions)**

The investigator will assess causality by answering either “yes” or “no” to the question “Is there a reasonable possibility that the event may have been caused by the IMP/study medication?”

##### **10.4.2.2.4. Severity/Intensity**

The intensity or severity of the PTAE or TEAE will be recorded using the following guidance:

- Mild (awareness of sign or symptom, but easily tolerated)
- Moderate (discomfort sufficient to cause interference with normal activities)
- Severe (incapacitating, with inability to perform normal activities)
- Life-threatening (urgent intervention indicated)
- Fatal (event led to death)

#### **10.4.2.2.5. Seriousness**

A PTAE or TEAE that meets any of the criteria for an SAE outlined in [Section 10.4.1.3](#) will be recorded as an SAE, along with the criteria that were met.

It is important to distinguish between seriousness (PTAE or AE compared with SAE) and severity/intensity (mild, moderate, severe, life-threatening, or fatal) of AEs as outlined in [Section 10.4.1.3](#).

#### **10.4.2.2.6. Outcome**

The outcome of a PTAE or TEAE will be recorded according to the options provided on the eCRF.

#### **10.4.2.3. Reporting of Serious Adverse Events**

All SAEs occurring during the treatment-emergent period (defined as the period from the first dose of study drug to the last dose of study drug + 56 days), regardless of causality, will be reported by the investigator or designee to MyoKardia or their designee within 24 hours of knowledge of the event or sequelae. Deaths and SAEs occurring after the treatment-emergent period and considered related to study drug or study procedure must also be reported. SAE reporting instructions are provided in the Study Reference Manual.

Medical records may be requested to support documentation of an SAE. The investigator is responsible for summarizing the pertinent aspects of the event (including discharge summaries, diagnostic procedures, laboratory data, interventions) and updating the SAE eCRF with this information.

MyoKardia or their designee retains the right to request additional information for any participant with any ongoing AEs/SAEs at the end of the study, if judged necessary.

Spontaneously reported SAEs after completion of the study should be promptly reported by the investigator to MyoKardia or their designee.

Prompt notification by the investigator to MyoKardia or their designee of SAEs is essential so that legal obligations and ethical responsibilities for the safety of participants and the safety of a study intervention under clinical investigation are met.

